6.2 Image Attribute Review Data

Following training (see Section 7. Qualification and Training Plan), readers will evaluate all image sets from all cases by classifying each of the following image attributes as either “Acceptable” or “Not Acceptable” on CRFs.

- 1) Breast positioning, assessing coverage of the breast on craniocaudal and mediolateral oblique view, separately
- 2) Exposure, assessing visualization of the adipose and fibroglandular tissues, and visualization of breast tissue underlying the pectoralis muscle, separately
- 3) Breast compression, assessing overlapping breast structures, uniformity of exposure of fibroglandular tissues, adequacy of penetration of thicker portions of the breast, and exposure of thinner areas
 - a. If you answered “not acceptable,” was breast compression acceptable or not? If not, would you request repeat imaging in standard clinical practice? Yes or No.
 - b. If you answered “not acceptable,” was there another reason it was unacceptable? If not, would you request repeat imaging in standard clinical practice? Yes or No.
- 4) Sharpness due to motion
 - a. If you answered “not acceptable,” would you request repeat imaging in standard clinical practice? Yes or No.
- 5) Image contrast for differentiation of subtle tissue density differences
- 6) Sharpness, assessing the edges of fine linear structures, tissue borders, and benign calcifications
- 7) Tissue visibility at the skin line
- 8) Noise, i.e., noise obscuring breast structures or suggestive of structures not actually present
- 9) Artifacts due to image processing, detector failure and other factors external to the breast on hard-copy and soft-copy displays
- 10) Overall clinical image quality
 - a. If you answered “not acceptable” for overall clinical image quality, would you request repeat imaging in standard clinical practice? Yes or No.
 - b. If yes, which view would you request for repeat imaging? CC only, MLO only, or both CC and MLO?

If an issue is encountered by any reader during the image attribute review of any image set, an explanation of the issue will be documented on a CRF by the reader.

Readers will also classify the breast density of each image set as follows:

- 1) Almost entirely fatty
- 2) Scattered areas of fibroglandular density
- 3) Heterogeneously dense
- 4) Extremely dense

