3.2.2 Secondary Endpoints

The secondary endpoints are:

- Number of incidences per image set when the technologist and/or readers indicate a repeat acquisition for PAC and TC compression; and
- Acceptability of mammographic attributes, as defined in the *Guidance* and as described in Section 6.2 Image Attribute Review Data.

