5.3.2 Image attribute review

Following acquisition, study-specific 3D images will be de-identified, and the time stamp, compression force, and breast thickness will be removed from the DICOM header to ensure the readers are blinded to the compression mode used for each image set. The image sets will be randomized for presentation during the image attribute reviews.

The 3D PAC and TC compression image sets will be evaluated by two (2) MQSA-qualified readers, with a third reader to provide adjudication if disagreement is observed between the two (2) readers' evaluations of "overall clinical image quality" (i.e. item number 9 in Section 5.3.2 Image attribute review). Images will be displayed on site-provided mammography review workstations/systems per the previously defined randomization scheme. Each reader will evaluate each image set independently from other reader(s) and have the freedom to navigate between views, as he/she would do in clinical practice.

In addition to the images, the following case data will be available to the readers for each image set during image attribute review:

- Techniques (anode, filter, kVp, mAs, half-value layer)
- Estimated average glandular dose per view (mGy)

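### Reader-form item 3b opens the repeat-imaging question on an inverted condition, so some reader repeat requests can go unrecorded; the adjudication rule also cites the wrong item

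*Combined protocol and SAP*

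**What the plan says.** Section 6.2 lists ten attributes, each rated acceptable or not acceptable. Repeat-imaging questions are attached to three of them.

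- **Item 3, breast compression.** A rating of not acceptable leads to two sub-questions. Item 3a asks "was breast compression acceptable or not? If not, would you request repeat imaging in standard clinical practice". Item 3b asks "was there another reason it was unacceptable? If not, would you request repeat imaging in standard clinical practice".
- **Item 4, sharpness due to motion.** Item 4a asks the repeat question after a rating of not acceptable.
- **Item 10, overall clinical image quality.** Item 10a asks the repeat question only if overall quality was rated not acceptable, and 10b then asks for the view.

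Item 1 (positioning) has no repeat question.

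These answers supply the reader part of the first secondary endpoint in Section 3.2.2: "Number of incidences per image set when the technologist and/or readers indicate a repeat acquisition for PAC and TC compression". Section 10.3.3 summarises that endpoint as a proportion of image sets for each mode. Neither section says how the answers to 3a, 3b, 4a and 10a are combined.

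Section 5.3.2 sends reader disagreement on overall clinical image quality to a third reader and identifies the attribute as "item number 9 in Section 5.3.2 Image attribute review".

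**The concern.** The condition in 3b runs the wrong way. A reader who had another reason for failing item 3 is the one who should be asked whether that reason warrants a repeat, yet the question opens only for a reader who had none. Item 3a does not clearly compensate, because its wording puts the rating just given to the reader a second time.

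At stake is the completeness of the reader data on the need for repeat acquisition. A question the form never asks cannot be recovered in the analysis, and Section 10.4 plans no imputation. The reader form also carries weight here because the technologist questions in Section 6.1 differ by mode: for PAC the technologist says whether a repeat would have been done, for TC whether one was done.

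The item reference in the adjudication rule is a separate, smaller slip, but it sits in the rule that settles the primary endpoint.

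**Working it through.** The plan gives no figure to reproduce on this point. The check traces the branches of the form and compares the cross-reference with the item list.

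**Step 1. Item 3 when 3a separates compression itself from other causes.** This reading is plausible because item 3 bundles overlapping structures, uniformity of exposure, penetration and exposure of thin areas. The reader has rated item 3 not acceptable. As written, 3a opens the repeat question if compression itself was at fault, and 3b opens it if there was no other reason. Each opening counts as 1.

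| Reason for failing item 3 | 3a | 3b | Item 3 total | With 10a, overall acceptable | With 10a, overall not acceptable |
|---|---|---|---|---|---|
| Compression only | 1 | 1 | 2 | 2 | 3 |
| Other reason only | 0 | 0 | 0 | 0 | 1 |
| Both | 1 | 0 | 1 | 1 | 2 |
| Neither | 0 | 1 | 1 | 1 | 2 |

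In the second row with overall quality acceptable, neither item 3 nor item 10 asks about a repeat. In the third row the question opens only through 3a, so the other reason gets no repeat question of its own.

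**Step 2. The same table with the 3b condition reversed.** The item 3 totals become 1 (compression only), 1 (other only), 2 (both, one per reason) and 0 (neither). The fault is therefore the direction of a single condition.

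**Step 3. Item 3 when 3a merely repeats the rating.** Every reader who failed item 3 again answers that compression was not acceptable, so 3a always opens the repeat question. Nothing is lost at item 3; 3b only adds a duplicate when there is no other reason. The loss in step 1 therefore depends on the first reading of 3a.

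**Step 4. Other routes.** Item 4a covers motion only. Item 10a covers any cause, but only when overall quality fails. A reader who would repeat for positioning on a set rated acceptable overall has nowhere to say so. Items 2 and 5 to 9 also lack a repeat question; positioning stands out because Section 6.1 lists it first among the technologist's reasons for repeating.

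**Step 5. Size.** Section 10.2 plans 30 image sets per mode. One set is 1/30 = 0.033, or 3.3 percentage points. A missed request moves the proportion by that much only if no other source contributing to the endpoint flags the same set. The documents give no basis for estimating how often this occurs.

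**Step 6. Count or proportion.** If the endpoint is the count in Section 3.2.2, a compression-only failure can be entered more than once by the same reader (row 1). If it is the proportion in Section 10.3.3, a set with several yes answers is still one set.

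**Step 7. Cross-reference.** Section 5.3.2 contains no numbered attribute list. In Section 6.2 the ninth entry is "9) Artifacts due to image processing, detector failure and other factors external to the breast" and the tenth is "10) Overall clinical image quality". The correct reference is item 10 in Section 6.2.

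**The case against.** The strongest reply is that calling 3a circular and saying that requests are lost rest on different readings of 3a. That is right: if 3a is circular, no item 3 failure escapes the repeat question. The loss holds only if 3a discriminates between causes, and the documents do not say which was meant. It also needs a failure for another reason only, overall quality rated acceptable, and a reader who would still ask for a repeat. Item 10a, item 4a and the technologist form, which lists positioning for both modes, narrow it further. Training in form completion is planned (Sections 6.2, 7.2 and 11.1.1), and readers may guess the intent. All of this limits the size of the problem. It does not make the 3b condition correct.

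Three stronger readings are tempting, and the documents do not support them.

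- *A reader might infer that duplicate answers inflate the repeat result.* They would inflate a raw count under Section 3.2.2. They do not change the proportion of image sets that Section 10.3.3 plans to report.
- *A reader might infer that the form biases the PAC versus TC comparison, because compression control is what differs between the modes.* Readers are blinded, presentation is randomised, and the same form serves both modes (Sections 1.2 and 5.3.2). A differential effect would need a different mix of failure reasons by mode, which nothing in the documents establishes.
- *A reader might infer that disagreements on the primary endpoint would go unadjudicated.* Section 5.3.2 and the synopsis both name overall clinical image quality in words. The wrong number would matter only if it were programmed literally, and the electronic form is not in the documents.

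**Conclusion.** The point holds in a limited form. The condition in 3b is inverted as written, 3a is unclear, and item 1 has no reader repeat question. If 3a is read as separating compression from other causes, an other-reason-only failure on a set rated acceptable overall yields no repeat answer under items 3 or 10. Repeat requests for positioning on such sets are unrecorded under either reading of 3a.

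Each affected set is worth up to 3.3 points of a 30-set proportion. The number of affected sets is unknown and may be zero. The exposure is confined to the reader part of the repeat-acquisition secondary endpoint. The study tests no hypothesis, so no error rate is involved. The wrong item reference in Section 5.3.2 is a minor correction. The form should be corrected before the reads, because the cost is small and unasked questions cannot be recovered afterwards.

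**What to change.** Before the reads start:

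1. Replace 3a and 3b with one entry: *If not acceptable, give the reason(s): compression / other (specify). Would you request repeat imaging? Yes or No.* The repeat question then opens whatever the reason.
2. Add the same repeat question to item 1.
3. State the derivation rule: for each reader, an image set counts at most once, as indicated for repeat if any of items 1, 3, 4a or 10a is yes. This agrees with the proportion in Section 10.3.3 and removes the effect of duplicate answers. Align the endpoint wording in Section 3.2.2 with it.
4. In Section 5.3.2, cite item 10 in Section 6.2 for overall clinical image quality.

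The cost is a small change to form wording and electronic branching, plus a few added sentences in the protocol. No extra images or readers are needed.

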6.3 Safety Assessments

The description, severity, and device relatedness of any AE or SAE during the study will be recorded. Subjects will, if necessary, be provided with emergency care. In the event of any device issues, the event will be recorded. Safety reporting will be conducted as described in this protocol.

7. QUALIFICATION AND TRAINING PLAN

7.1 Staff Qualifications

All members of the study staff participating in the conduct of the clinical investigation shall be qualified by education, training and/or experience to perform their tasks, and this shall be documented appropriately, as per ISO 14155:2011. Specifically, readers shall be MQSA-qualified.

7.2 Training Plan for the Protocol and Research Product

Before starting the study, study staff will be trained on the requirements and procedures set forth in this study protocol, including completion of ICFs, CRFs, and other study documentation. Training will also be provided to ensure appropriate storage and handling of data, and all study staff will be required to be trained on Good Clinical Practice (GCP) guidelines per ISO 14155: 2011.

A record of all formal training will be stored in the Site Regulatory Binder and provided to the Sponsor for inclusion in the Sponsor's CHF. Documentation of training will include:

- Title of Training
- Training objectives
- Training logistics (trainer and training methods)
- Documentation of trainees
- Training content (e.g. device operation, protocol review and CRF completion)

Study staff directly operating the PAC product will be qualified based on mammographic experience and trained to use PAC by a GE application specialist.

The Principal Investigator will be ultimately responsible for execution of this study in accordance with the protocol and for device use in this study by members of the study staff.

8. SAFETY

8.1 Anticipated Adverse Events

Mammography is an x-ray examination of the breasts. As with all x-ray exams, mammography involves ionizing radiation. The amount of radiation from a standard screening mammography exam, even with the addition of the study-specific unilateral, two-view imaging, is small and equal in cancer risk to the total body radiation received naturally from the environment over a period of a few months.

There are no known additional medical risks or side effects from Senographe Pristina 3D with PAC mode beyond those of similar conventional clinical procedures on other commercial mammography devices. Foreseeable AEs that apply to mammography and are also applicable to digital mammography using Senographe Pristina 3D with PAC may include, but are not limited to:

- Bruising (uncommon);
- Skin irritation (uncommon), abrasions (uncommon), or tears (rare);
- Discomfort (common).

The study staff conducting the research is trained to recognize these reactions, and should it be necessary, other medical care is available at the site. Subjects will be followed for AEs from the time they enter the imaging suite for their exam until the time they exit the imaging suite after the exam.

It is generally agreed that the risk to a fetus from radiation in a screening mammography exam is minimal¹⁹; however, it is standard clinical practice to try to determine pregnancy status of women referred for mammography and not allow

women known or suspected to be pregnant to undergo screening mammography or other elective radiologic procedures.

There is always a chance of unexpected risks. Throughout the study, the Sponsor will evaluate and update safety information in study documents.

8.2 Adverse Event Definitions

Adverse Event (AE): any untoward medical occurrence, unintended disease or injury, or untoward clinical signs (including abnormal laboratory findings) in subjects, users or other persons, whether or not related to the investigational medical device [ISO 14155:2011 3.2]. This includes events related to the investigational device or the comparator and to the procedures involved. For users or other persons, this is restricted to events related to the investigational medical device.

Serious Adverse Event (SAE): an adverse event that led to death; led to a serious deterioration in the health of the subject, that either resulted in a life-threatening illness or injury, a permanent impairment of a body structure or a body function, or in-patient or prolonged hospitalization, or medical or surgical intervention to prevent life-threatening illness or injury or permanent impairment to body structure or a body function; or led to fetal distress, fetal death or a congenital abnormality or birth defect. Planned hospitalization for a pre-existing condition, or a procedure required by the protocol without serious deterioration in health, is not considered a SAE [ISO 14155:2011 3.37].

Adverse Device Effect (ADE): an adverse event related to the use of an investigational medical device [ISO 14155:2011 3.1]. This includes any adverse events resulting from insufficient or inadequate instructions for use, deployment, implantation, installation, or operation, or any malfunction of the investigational medical device. This includes any event that is a result of a user error or intentional misuse of the investigational device [ISO 14155:2011 3.43].

Serious Adverse Device Effect (SADE): an adverse device effect that has resulted in any of the consequences characteristic of a serious adverse event [ISO 14155:2011 3.36].

Device deficiency: an inadequacy of a medical device with respect to its identity, quality, durability, reliability, safety, or performance, such as malfunctions, use errors, and inadequate labelling [ISO 14155:2011 3.15].

Unanticipated serious adverse device effect (USADE): a serious adverse device effect, which by its nature, incidence, severity, or outcome has not been identified in the current version of the risk analysis report [ISO 14155:2011 3.42]. In the United States, any serious adverse effect on health or safety or any life-threatening problem or death caused by, or associated with, a device, if that effect, problem, or death was not previously identified in nature, severity, or degree of incidence in the study documents, will be reported in accordance with 21 CFR §812.3 and applicable laws and regulations.

8.3 Documentation of Safety Events

All adverse events (AE), including all serious adverse events (SAE), are required to be collected, investigated, and documented during the study reporting period, as defined in the study procedure set forth in this protocol. Documentation will include:

- Description of Event
- Date of onset and resolution
- Severity (mild, moderate, or severe)
 - *Mild:* Symptom(s) barely noticeable to the subject or does not make the subject uncomfortable. The AE does not influence performance or functioning. Prescription drugs are not ordinarily needed for relief of symptom(s).
 - *Moderate:* Symptom(s) of a sufficient severity to make the subject uncomfortable. Performance of daily activities is influenced. Treatment of symptom(s) may be needed.
 - *Severe:* Symptom(s) of a sufficient severity to cause the subject severe discomfort. Treatment for symptom(s) may be given.

- Serious (yes/no)
- Causal relationship to investigational medical device? (not related, possibly related, or related)
 - *Not related:* The adverse event is reasonably expected to be related to (or caused by) a concurrent illness, effect of another device/drug or other cause, and is unlikely related to the investigational product.
 - *Possibly related:* The adverse event is reasonably expected to be related to the investigational product, and an alternative etiology is equally or less likely compared to the potential relationship to investigational product.
 - *Related:* There is a strong relationship to investigational product or recurs on re-challenge, and another etiology is unlikely or there is no other reasonable medical explanation for the event.
- Treatment given and/or action taken (procedure stopped, withdrawn from study, or no action)
- Anticipated (yes/no)

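### The 8.3 severity grades leave a gap for ordinary discomfort, and the listed AE fields record neither breast nor compression mode, so AEs cannot be reliably separated between PAC and TC

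*Combined protocol and SAP*

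**What the plan says.** **Expected events and window.** Section 8.1 names bruising, skin irritation, abrasions, tears and discomfort. Only the last is labelled common, in the entry that begins "Discomfort (common"; the others are uncommon or rare. The same section limits observation: "Subjects will be followed for AEs from the time they enter the imaging suite for their exam until the time they exit the imaging suite". The footnote to Table A.1 sets the same kind of limit (the exam room), and Section 5.4 plans no follow-up.

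**Grades (Section 8.3).**
- Mild: "Symptom(s) barely noticeable to the subject or does not make the subject uncomfortable", and "The AE does not influence performance or functioning".
- Moderate: "Symptom(s) of a sufficient severity to make the subject uncomfortable. Performance of daily activities is influenced".
- Severe: "Symptom(s) of a sufficient severity to cause the subject severe discomfort".

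**AE record (Section 8.3).** Seven items are listed: description, dates of onset and resolution, severity, seriousness, causal relationship to the investigational device, treatment or action, and whether the event was anticipated.

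**Devices and sequence.** Section 2.1 names the investigational device as PAC together with Senographe Pristina 3D. Section 2.4 names the comparator as the TC mode of that same system. The synopsis (Procedures/Methods) has the breast of interest imaged in two views with PAC and then in two views with TC; the other breast is imaged per standard of care.

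**Endpoint and analysis.** Section 3.2.4 defines the safety endpoint by type and number of events. Section 10.3.4 plans listings and a descriptive summary, with no split by mode.

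**The concern.** The event most likely to be recorded is discomfort from compression that ends on release. If the scale has no clear place for it, two technologists can grade the same event differently with nothing in the protocol to settle it, and the severity column of the listing loses meaning for the commonest event.

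The second issue is attribution. Section 1.1 presents PAC as a way to reduce pain and discomfort, and the study is meant to support submissions for PAC with 3D imaging. Neither 6.1 nor 6.2 includes a pain or discomfort measure, so the AE record is the only listed place where discomfort would appear. A reader of the listing will want to know whether an event arose under PAC or TC, and the listed items do not reliably say.

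**Working it through.** No rate, power or interval enters this point, and the plan states no figure for it. The check applies the definitions to cases and then inspects the record items.

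**Step 1: the grades applied to cases.** Describe a symptom by four yes/no features: barely noticeable, uncomfortable, severe discomfort, daily activities influenced. Apply the Section 8.3 wording in two ways. In the full reading, the symptom sentence and the function sentence must both hold. In the lead-sentence reading, only the first sentence of each grade counts.

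| Barely noticeable | Uncomfortable | Severe | Activities influenced | Full reading | Lead sentence only |
|---|---|---|---|---|---|
| yes | no | no | no | mild | mild |
| yes | yes | no | no | mild | mild |
| no | no | no | no | mild | mild |
| no | yes | no | no | **none** | moderate |
| no | yes | no | yes | moderate | moderate |
| no | yes | yes | no | severe | severe |
| no | yes | yes | yes | severe | severe |

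The table omits contradictory cases (severe yet barely noticeable) and those where a symptom that is barely noticeable or not uncomfortable affects activities, which is not ordinary discomfort. Of the seven cases, one has no grade on the full reading and none is ungraded on the lead-sentence reading.

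**Step 2: is the empty case likely?** It is discomfort that is plainly felt, not severe, and without effect on daily activities. Because observation ends at the suite door and there is no follow-up, an effect on daily activities can hardly be seen in time. Ordinary compression discomfort therefore tends to fall in this case. The documents give no discomfort rate, so the number of affected events cannot be estimated.

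**Step 3: can the record separate PAC from TC?**
- Items that name breast, view, compression mode or clock time: 0 of 7.
- Onset is recorded by date. PAC and TC fall in one exam, so the date cannot distinguish them.
- Items that bear on PAC indirectly: one, the causal relationship. Its device name includes the system that also delivers TC. If PAC and TC are equally plausible causes, the 8.3 definition gives possibly related, because it allows an equally likely alternative. A TC-caused event could be called not related (device read as PAC) or related (device read as the Pristina 3D system).
- Section 8.2 counts comparator events as AEs, yet no item asks for relatedness to TC.
- The free-text description may mention the mode, but nothing requires it.

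**Step 4: comparison with the rest of the plan.** Section 6.1 asks separate PAC and TC questions about repeat acquisition, and 3.2.3 collects the exploratory endpoints for each compression. The AE items have no such separation.

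**The case against.** A reader might infer that the scale cannot grade discomfort at all, that such events would go unrecorded, and that the safety endpoint therefore cannot describe PAC. The documents do not support this.

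- Mild is worded as an alternative, so barely noticeable discomfort fits it. Severe carries no function criterion, so severe discomfort can be graded.
- Section 8.3 requires every AE to be documented, whatever the doubt about its grade.
- The endpoint in 3.2.4 does not use severity.
- The causal-relationship item and the description give some link to PAC.
- No PAC-versus-TC safety comparison is planned, and Section 3.1 ties the study's purpose to image quality and workflow.

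These points stand and set the limits of the concern.

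It can also be argued that the function sentence is a descriptor rather than a condition, since neighbouring sentences on treatment are hedged. This is a fair reading, and it closes the gap. But the function sentence is not hedged: "Performance of daily activities is influenced" is stated flatly, it mirrors an equally flat sentence under mild, and nothing tells the site to disregard it.

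The sponsor's right in 8.4 to request more information does not fill the attribution gap for discomfort. It follows a list of SAEs, USADEs and device issues that could lead to an SAE. The AE form itself is not among the documents, so a mode field on it cannot be ruled out.

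**Conclusion.** The point holds in two limited parts.

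1. The mild and moderate definitions leave one case without a clear grade. It is a likely form of the only AE called common. This assumes that the sentence on daily activities is a criterion; read as a descriptor, the case is moderate.
2. With the listed items, AEs on the breast of interest cannot be reliably separated between PAC and TC. This can arise in every subject who completes imaging (30 targeted, up to 36 enrolled), because each receives both modes on the same breast. It assumes that the AE form contains no more than 8.3 lists.

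The overall count and type of AEs are unaffected, as are the primary and secondary endpoints. What is not assured is a consistent severity grade for ordinary discomfort, or a listing that can be read by mode. The mode at a brief in-exam event cannot be reliably recovered later, so the change belongs before enrolment.

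**What to change.** - **Section 8.3, grades.** Make them exhaustive for discomfort: let moderate cover discomfort that is clearly felt but not severe, without requiring an effect on daily activities.
- **Section 8.3 and the AE form.** Add two required items: breast (breast of interest or other), and compression at or before onset (PAC CC, PAC MLO, TC, none or unclear). This matches the separate PAC and TC questions already on the acquisition form in 6.1.
- **Section 10.3.4.** List AEs by these two items. No formal comparison is needed.

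The cost is some protocol wording, slightly more AE form work and a changed listing layout. The repair is incomplete: an event first noticed after both compressions, such as bruising, will still be of unclear attribution and should be recorded as such.
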